7.3.2.7 Effectiveness Variables

- Longitudinal serum biochemical parameters, including pre- and post-odevixibat treatment changes (as far as available) of AST, ALT, ALP, total bilirubin, direct bilirubin, GGT, INR, albumin, creatinine, sodium, platelet count, and serum bile acid levels
- Clinical outcomes: surgical biliary diversion, liver transplantation, and overall survival

PAGE 31 OF 76

• Clinical symptoms: pruritus and sleep disturbance, if (semi-) objective scoring data are available

7.3.2.8 Treatment Variables

The registry-based study will collect the following data on odevixibat treatment at the Baseline Visit and at the Follow-up Visits if available:

- Odevixibat start date, dosage, and treatment end date
- Reasons for dose modification/treatment discontinuation

7.4 Data Sources

Source data include any data collected as part of routine medical care which will be captured in an eCRF by the investigator and transmitted to the sponsor for analysis.

7.5 Study Size

No formal sample size calculations have been performed for this registry-based study.

Enrolment will be based on the number of participants prescribed odevixibat and their willingness to participate in the study, but the goal will be to enroll approximately 30 to 45 participants with ALGS.

7.6 Data Management

Data management will be conducted by a Service Provider (SP) directed by the sponsor's Global Medical Affairs Biometry Department. All data management procedures will be completed in accordance with the Standard Operating Procedures (SOPs) of Ipsen and the contracted SP.

7.6.1 Data Collection

The specific data to be collected at each visit, if available, are summarized in the schedule of assessments (Table 1).

All relevant data collected as part of routine medical care will be captured using the eCRF by the investigator and transmitted to the sponsor. If some assessments included in the protocol are not routinely performed by the investigator, the corresponding sections in the eCRF do not need to be completed.

Data will be collected in an eCRF via the internet utilizing a secured website. The sponsor and the SP will ensure that the eCRF developed is appropriate to capture the data required by the protocol. The sponsor will ensure that the entrusted SP uses adequate technology to ensure data security transfer and backup.

Each site is required to have a computer and internet connection available for site entry of clinical data. Data entry in the eCRF will be performed by the investigator or by the designated person from their team and to ensure confidentiality and security of the data, all entries into the eCRF will be made under the electronic signature (e-signature) of the person performing the action (username and password). Only sponsor-authorized users will be given access to the eCRF as appropriate for their study responsibilities. All users must have successfully undergone software application training prior to entering data into the eCRF.

Once the signed informed consent (and assent, if applicable) has been obtained, the eCRF will provide a numeric participant identifier to pseudonymize the data from each participant. Data for each participant must be entered into the eCRF within 5 days of the participant's enrolment and each Follow-Up Visit. Data transmitted will be pseudonymized and will be identified only by the participant number. Only investigating sites will be able to link the numeric identifier to each participant's identity.

PAGE 32 OF 76

In compliance with Good Pharmacoepidemiology Practices (GPP), the participant's medical records should be clearly marked and permit easy identification of their participation in this registry-based study.

Medical and surgical history, concomitant surgeries, Special Situations, and AE terms will be coded using the Medical Dictionary for Regulatory Activities (MedDRA) and prior/concomitant medication and vitamin supplementation will be coded using the World Health Organization Drug Dictionary by the contracted SP and reviewed by the sponsor.

Queries will be addressed to the investigational site using the eCRF.

Investigators or authorized study staff members will answer the queries directly into the eCRF. The eCRF will be signed electronically by the investigator to certify that all the data recorded in it are consistent with the source documents and reflect the status of the participant during the corresponding part of the study.

7.6.1 Data Archiving and Retention

During the site initiation visits, the monitor must ensure that the archiving facilities are adequate and archiving/retention responsibilities of the investigator have been discussed.

Study documents should be retained for at least 10 years after study completion. However, these documents should be retained for a longer period if required by the applicable regulatory requirements or by agreement with the sponsor. The investigator should take measures to prevent accidental or premature destruction of these documents. The final archiving arrangements will be confirmed by the monitor when closing out the site. The sponsor will inform the investigator, in writing, as to when these documents no longer need to be retained.

If the investigator relocates or retires, or otherwise withdraws their responsibility for maintenance and retention of study documents, the sponsor must be notified (preferably in writing) so that adequate provision can be made for their future maintenance and retention.

7.7 Data Analysis

7.7.1 Analyses Population Definitions

Safety Population: all participants who have taken at least one dose of odevixibat following enrolment.

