7 RESEARCH METHODS

7.1 Study Design

This will be a long-term, observational, prospective, and voluntary participation registry-based study designed to collect and assess real-world data on participants with ALGS chronically treated with odevixibat.

The study population will comprise participants with ALGS treated with odevixibat enrolled into the registry-based study. Participants who started odevixibat treatment before the implementation of the registry-based study may also be enrolled.

As this is an observational study designed to assess real-world data, the decision to prescribe the product must be taken prior to, and independently from, the willingness of the participant to be included in the registry-based study. This decision should be made in accordance with routine/standard clinical practice. The assignment of the participant to a particular therapeutic strategy is not decided in advance by the study protocol but falls within current practice.

Participants will be treated and monitored in accordance with usual medical practice during their participation in this registry-based study. No additional assessments or tests will be required by this protocol. All relevant data collected as part of routine medical care will be captured using the electronic Case Report Form (eCRF) by the investigator and transmitted to the sponsor. If some assessments included in this protocol are not routinely performed by the investigator, the corresponding sections in the eCRF do not need to be completed.

This registry-based study will collect data at Baseline and at each Follow-up Visit. Follow-up Visits are scheduled as per routine clinical practice (expected to occur at least every 6 months or more frequently, based on the investigator's judgement).

The duration of this registry-based study is approximately 5 years. Following enrolment, participants will continue to participate in the study for ≥ 2 years or until the time point of withdrawal of consent, for up to 180 days after last dose of odevixibat (in case of treatment discontinuation), death, the end of data collection, or the sponsor decides to discontinue the study.

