7.2 Setting

7.2.1 Inclusion Criteria

To be included in the registry-based study, the participant should fulfil the following inclusion criteria:

- (1) Diagnosed with ALGS.
- (2) On (or starting) active odevixibat treatment.
- (3) Signed informed consent and assent, as appropriate. Consent/assent from the participant or legal representative should be obtained, as appropriate, before any study data collection is conducted. Participants who turn 18 years of age (or legal age per country) while participating in the study will be required to provide consent for themselves.

PAGE 23 OF 76

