7.2.8 Study Discontinuation/Withdrawal

The participant can withdraw (or be withdrawn if the participant is a child upon legal representative's decision) from this registry-based study at any time. The date and primary reason for withdrawal should be recorded in the eCRF as well as if the participant stopped odevixibat or not.

For study results to remain unbiased, it is important that no data are modified; as a result, the data collected in clinical studies need to remain untouched for results to be trusted. Should the participant withdraw from the study, no further data will be collected; nevertheless, data collected up to the time of the withdrawal will be kept for analysis, safety, and integrity of study results.

PAGE 28 OF 76

The participant will be withdrawn from the registry-based study if:

- They enroll in any interventional clinical trial
- The participant is no longer receiving odevixibat and has completed the last follow-up visit up to 180 days after last dose of odevixibat (see Section 9.4 for follow-up of AEs and Section 9.1.3.1 for follow-up of pregnancies)

Note: Participants can remain in the registry-based study during odevixibat treatment interruptions.

Investigators may decide to stop their participant's participation in the study at any time without consequences on the normal participant follow-up.

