7.2.9 Treatment Discontinuation

Odevixibat treatment may be discontinued based on the judgement of the treating physician, including in the event of any serious adverse events (SAEs), AEs, or Special Situations (see Section 9.1.3 for definition of Special Situations) deemed by the investigator to warrant treatment discontinuation. In the event of pregnancy, odevixibat treatment may be discontinued based on the judgement of the treating physician (Section 9.1.3.1).

Discontinuation of treatment due to **AEs** should be distinguished discontinuation/withdrawal from the study due to participant/parent decision or end of followup.

If AEs or their sequelae (any AE, based on the investigator's opinion, not only those assessed as related) persist after the date of odevixibat discontinuation the investigator must ensure that the participant receives appropriate medical follow-up and this should be properly documented in the participant's medical records.

All participants discontinuing odevixibat treatment will be followed up to 180 days after last odevixibat dose (unless consent is withdrawn) or until the end of data collection, whichever comes first.

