7.3.1.1 Primary Endpoints

- Incidence of biliary diversion surgery, liver transplantation, or death in participants with ALGS chronically treated with odevixibat.
- Surgical biliary diversion-free survival, defined as time from the start of odevixibat treatment to the first occurrence of surgical biliary diversion or death.
- Liver transplant-free survival, defined as time from the start of odevixibat treatment to the first occurrence of liver transplant or death.
- Overall survival, defined as time from the start of odevixibat treatment to death.

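### The only defined analysis population requires a dose after enrolment, so an already-treated enrolee who takes no further dose falls outside it

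*Protocol*

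**What the plan says.** Section 7.7.1 of the Protocol gives a single population: "Safety Population: all participants who have taken at least one dose of odevixibat following enrolment". No other analysis set is defined in the Protocol.

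Other sections describe who enters and how they are observed:

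- **Entry.** Inclusion criterion 2 (Section 7.2.1) reads "On (or starting) active odevixibat treatment", and Section 7.1 adds "Participants who started odevixibat treatment before the implementation of the registry-based study may also be enrolled".
- **Time origin.** The three time-to-event primary endpoints in Section 7.3.1.1 run from first treatment, for example "Overall survival, defined as time from the start of odevixibat treatment to death". For an already-treated participant that date is before enrolment.
- **AE window.** Table 1 (footnote k) and Sections 7.3.2.6 and 9.2.1 collect AEs from the signing of consent until 180 days after the last dose. The window does not wait for a dose after enrolment.
- **Interruption.** Section 7.2.8 notes "Participants can remain in the registry-based study during odevixibat treatment interruptions".
- **Stopping.** Section 7.2.9 states "All participants discontinuing odevixibat treatment will be followed up to 180 days after last odevixibat dose", subject to withdrawal of consent or the end of data collection.

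**The concern.** Requiring a dose after enrolment is natural where treatment begins after enrolment, because it then removes only the never-exposed. In a registry that takes in people already on the drug it does something else: it also removes exposed people who do not continue. Membership then depends on something that happens after entry, namely continued dosing, and this can be related to outcome. Section 7.2.9 names SAEs and other AEs among the grounds for discontinuing. One secondary endpoint (Section 7.3.1.2) is suspected hepatotoxicity requiring interruption of treatment. A participant with that event straight after consent, who takes no further dose, would be left out of the population because of the event being counted.

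At stake are the incidence of diversion, transplant or death, the survival summaries and the AE incidences, in a cohort planned at only about 30 to 45 (Section 7.5).

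**Working it through.** The Protocol states no calculated sample size, expected event rate or number of already-treated enrolees, so there is no planned figure to reproduce. The check has two parts.

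**1. Applying the definition literally.** Take a participant on odevixibat at consent whose last dose is at or before enrolment and who does not restart.

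| Rule | Section | Result |
|---|---|---|
| On active treatment at entry | 7.2.1, 7.1 | can be enrolled |
| Primary clock starts at first dose | 7.3.1.1 | already running at enrolment |
| AEs collected from consent | Table 1, 7.3.2.6, 9.2.1 | under observation |
| Stays in during an interruption; followed up to 180 days after last dose if discontinued | 7.2.8, 7.2.9 | outcomes collected |
| At least one dose following enrolment | 7.7.1 | zero doses: outside the population |

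Four of the five rules treat this person as exposed and followed. Only Section 7.7.1 does not, and no other section brings the person back.

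**2. Size for one such participant.** The planned enrolment of 30 to 45 comes from Section 7.5. The event counts (5 of 30, 6 of 45) are assumptions made for illustration.

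Share of the cohort removed: 1/30 = 3.3%; 1/45 = 2.2%.

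With x events among n participants, the incidence is x/n. Dropping one participant with an event gives (x − 1)/(n − 1). Dropping one without an event gives x/(n − 1).

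| Cohort | All kept | One with event dropped | One without event dropped |
|---|---|---|---|
| n = 30, x = 5 | 5/30 = 16.7% | 4/29 = 13.8% | 5/29 = 17.2% |
| n = 45, x = 6 | 6/45 = 13.3% | 5/44 = 11.4% | 6/44 = 13.6% |

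In percentage points:

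- With an event: 16.67 − 13.79 = 2.88 lower at n = 30, and 13.33 − 11.36 = 1.97 lower at n = 45.
- Without an event: 17.24 − 16.67 = 0.57 higher, and 13.64 − 13.33 = 0.31 higher.

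**Direction in general.** If the dropped participant has event probability q, the expected incidence after the drop is (x − q)/(n − 1). This is below x/n when n(x − q) < x(n − 1), that is, when q > x/n. The exclusion therefore flatters the result only if those dropped carry more risk than the cohort average.

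**Against the sampling uncertainty.** The exact 95% interval for 5/30 is 5.6% to 34.7%, and for 4/29 it is 3.9% to 31.7%. The shift from one exclusion is small beside either interval.

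**The case against.** Four points can be made for leaving the text alone.

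- **Reach.** A reader might infer that these participants vanish from every table. The Protocol does not say so. Section 7.7.1 assigns its population to no particular analysis, Section 7.7.2 does not restrict the primary, growth or disposition summaries to it, and the SAP may map analyses to sets or add an enrolled set. This stands. What can be said is that they are outside the only population the Protocol defines.
- **Frequency.** Someone permanently off treatment before enrolment fails inclusion criterion 2, and one whose drug is stopped at the consent visit is a borderline case. A single later dose restores membership. This stands too: the group is narrow and may be empty.
- **Direction.** A reader might infer that the excluded participants are all stopping for toxicity, failure or transplant, and that each exclusion lowers the incidence. The documents support neither. Section 7.2.9 leaves stopping to the physician's judgement and does not confine the reasons to AEs, and dropping a participant without an event raises the incidence slightly. Informative exclusion is plausible, not shown.
- **Safety reporting.** Section 7.7.2.2 puts all AEs and Special Situations in the participant listings. Section 9.2.2 sends SAEs, related nonserious AEs and Special Situations to pharmacovigilance, and Section 9.7 provides ongoing review. AEs would therefore not be lost to view. But a listing supplies no incidence, and the primary endpoints are incidences and survival estimates.

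These points limit the size of the problem. None of them reconciles Section 7.7.1 with the sections on eligibility, time origin and follow-up.

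**Conclusion.** The point holds in a limited form. The definition in Section 7.7.1 does not fit a registry that admits people already on treatment: read literally, it leaves out an exposed, followed enrolee who takes no dose after enrolment. Because it conditions on continued dosing, it can be informative, most directly for suspected hepatotoxicity requiring interruption.

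Under the assumed counts, each excluded participant with an event lowers the incidence by about 2 to 3 percentage points, and each one without an event raises it by about 0.3 to 0.6. The number affected is not in the documents and could be zero. The analyses are descriptive, with no formal testing (Section 7.9), so no test result is at risk. This is a cheap improvement worth making, not a threat to the study. It concerns the analysis set only and takes no view on when treatment should be stopped or resumed.

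**What to change.** Redefine the population in Section 7.7.1 as all enrolled participants who have taken at least one dose of odevixibat, whether before or after enrolment. This excludes only those enrolled as starting treatment who never take a dose. State in the same place that this set is used for the primary, growth and AE summaries, and carry the wording into the SAP.

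The cost is a sentence or two. Treatment start and end dates are already collected (Section 7.3.2.8), so no new data are needed. The downside is that the set may gain a few participants with little on-treatment time in the study. How their time before enrolment enters the survival estimates (delayed entry) is a separate matter that this change does not settle.

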7.2.2 Exclusion Criteria

Participants will not be included in the registry-based study if:

- (1) Currently participating in a clinical trial with odevixibat.
- (2) Currently participating in any interventional clinical trial for ALGS.
- (3) Have any contraindication to odevixibat as per the locally approved label.
- (4) Had liver transplant before enrolment.

Individuals who do not meet the criteria for participation in this registry-based study (screen failure) or who withdraw their consent may be rescreened. Rescreened participants should be assigned a new participant number. The informed consent process is described in Section 7.13.

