7.3.1.2 Secondary Endpoints

• Growth and development in the form of height and weight (standard-deviation scores).

PAGE 29 OF 76

- Incidence of AEs associated with FSV deficiencies and their possible sequelae.
- Incidence of suspected hepatotoxicity requiring interruption of odevixibat treatment.
- Incidence of bleeding AEs, including events requiring emergency department care, hospitalization, or blood transfusion.
- All AEs, based on incidence, severity grade, causality, outcome, action taken, and seriousness.

7.3.2 **Variables**

Only the data collected as part of routine medical care will be captured using the eCRF by the investigator. If some assessments included here are not routinely performed by the investigator, the corresponding sections in the eCRF do not need to be completed.

Demographic and Baseline Characteristics 7.3.2.1

- Age, sex, weight, height, ALGS genetic variant, date of birth (MM/YYYY), and date of ALGS diagnosis
- General medical or surgical history
- Prior surgical procedures related to ALGS, including but not limited to prior biliary diversion surgery (date and type of surgery) and liver transplantation (date and donor information)
- Laboratory parameters, including ALT, AST, ALP, total bilirubin, direct bilirubin, GGT, INR, albumin, creatinine, sodium, platelet count, serum bile acid levels, and FSV levels. Historical values (the most recent values in the last 9 months prior to the first odevixibat dose) are also to be provided at baseline if available.
- Clinical symptoms: pruritus and sleep disturbance, if (semi-) objective scoring data are available. For non-naïve participants, the most recent values prior to the first odevixibat dose are to be collected.
- Pregnancy or breastfeeding status
- Planned biliary diversion surgery (planned date and indication)
- Listing for liver transplantation (planned date and indication)

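### The diversion endpoints have no at-risk restriction, so participants diverted before odevixibat dilute the crude diversion incidence

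*Protocol*

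**What the plan says.** **Eligibility.** Inclusion criterion 2 (section 7.2.1) is "On (or starting) active odevixibat treatment", and section 7.1 lets people enrol who began odevixibat before the registry opened. Section 7.2.2 has four exclusions. The only one that concerns an earlier outcome event is "Had liver transplant before enrolment". None mentions biliary diversion.

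**Baseline data.** Sections 7.2.7.1 and 7.3.2.1 collect prior surgery related to Alagille syndrome, and name earlier biliary diversion with its date and type. The odevixibat start date is collected too (sections 7.2.7.1 and 7.3.2.8).

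**Endpoints (section 7.3.1.1).** The first primary endpoint is "Incidence of biliary diversion surgery, liver transplantation, or death in participants with ALGS chronically treated with odevixibat". Surgical biliary diversion-free survival is "defined as time from the start of odevixibat treatment to the first occurrence of surgical biliary diversion or death".

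**Population and analysis.** Section 7.7.1 defines one population, the Safety Population: "all participants who have taken at least one dose of odevixibat following enrolment". Section 7.7.2.1 plans descriptive incidence and, where the data allow, Kaplan-Meier summaries. It names no population, sets no at-risk condition and does not say whether a repeat or revised diversion counts. Section 7.7.3 leaves possible subgroups to the SAP.

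**The concern.** Someone who already has a diversion when odevixibat starts cannot later have a first one in the ordinary sense. Nothing in the endpoint, population or analysis text removes that person from the diversion analyses. The participant therefore enters the denominator, and the Kaplan-Meier curve at time zero, as diversion-free.

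The protocol closes the matching gap for transplant through exclusion criterion 4 but leaves it open for diversion. Such participants are plausible. Section 5.3 gives the authorised use as cholestatic pruritus, and section 5.2 says that diversion is occasionally used for intractable pruritus.

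At stake is the meaning of a primary endpoint. A low diversion incidence may be read as surgery avoided on odevixibat, when part of it reflects people whose surgery had already taken place.

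**Working it through.** **1. The plan's own figure.** There is none. Section 7.5 states that no sample size calculation was done, and the protocol gives no expected diversion rate and no share with prior diversion. The only figure available is the enrolment goal of 30 to 45 (section 7.5). Everything else below is an assumption, shown over a range.

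**2. Diversion alone.** Let f be the share diverted before odevixibat and p the diversion risk in the others. If the previously diverted have no countable diversion, crude incidence = (1 − f) × p. With p = 10%:

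- f = 5%: 0.95 × 10% = 9.5%
- f = 20%: 0.80 × 10% = 8.0%

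The shift is 0.5 to 2.0 percentage points. One participant is 1/45 = 2.2 to 1/30 = 3.3 points, so the shift is less than one event.

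**3. The same in counts.** Four diversions are assumed, all in participants without prior diversion. The number removed is rounded to whole people. Intervals are exact (Clopper-Pearson) 95%.

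| Denominator | N = 30 | N = 45 |
|---|---|---|
| All participants | 4/30 = 13.3% (3.8–30.7) | 4/45 = 8.9% (2.5–21.2) |
| At risk, f = 5% | 4/28 = 14.3% (4.0–32.7) | 4/43 = 9.3% (2.6–22.1) |
| At risk, f = 10% | 4/27 = 14.8% (4.2–33.7) | 4/41 = 9.8% (2.7–23.1) |
| At risk, f = 20% | 4/24 = 16.7% (4.7–37.4) | 4/36 = 11.1% (3.1–26.1) |
| At risk, f = 30% | 4/21 = 19.0% (5.4–41.9) | 4/31 = 12.9% (3.6–29.8) |

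The ratio of crude to at-risk incidence runs from 43/45 = 0.96 to 31/45 = 0.69. Every at-risk estimate lies within the interval for all participants.

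**4. Diversion or death.** Let d be the death risk and k the relative risk of a countable repeat diversion. With equal death risk in both groups:

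mixed risk = (1 − f)[1 − (1 − p)(1 − d)] + f[1 − (1 − kp)(1 − d)]

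With p = 10%, d = 2% and f = 20%, the risk in those without prior diversion is 1 − 0.90 × 0.98 = 11.80%.

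- k = 0: 0.8 × 11.80% + 0.2 × 2.00% = 9.84%, ratio 0.83
- k = 0.5: 0.8 × 11.80% + 0.2 × 6.90% = 10.82%, ratio 0.92

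Over p = 5–15%, d = 2–5% and f = 5–30%, the ratio is 0.98 to 0.74 with k = 0 and 0.99 to 0.87 with k = 0.5.

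**5. Direction for the composite.** Step 4 assumes equal death risk. If the previously diverted have a different death risk d*, the dilution vanishes when 1 − (1 − kp)(1 − d*) = 1 − (1 − p)(1 − d). With p = 10% and d = 2%:

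- k = 0: d* = 11.8%
- k = 0.5: d* = 1 − 0.882/0.95 = 7.2%

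Above these values the composite would be raised, not lowered. The protocol gives no basis for choosing d*. Adding transplant, to which these participants also remain exposed, leaves the same uncertainty.

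**The case against.** **The SAP may deal with it.** Section 7.7.2 defers detail to a separate SAP, and section 7.7.2.1 does not name the Safety Population. A SAP could restrict the risk set, so one cannot say that these participants will in fact be analysed this way. What stands is narrower. Eligibility, event, time origin and sole population are all fixed in this protocol without restriction, and together they produce the problem unless something later undoes it.

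**No risk at all.** A reader might infer that previously diverted participants add person-time with no risk of a diversion event. The documents do not support that. The incidence endpoint does not use the word first. The phrase "to the first occurrence of surgical biliary diversion or death" can be read as the first diversion after odevixibat starts. Sections 7.2.7.2 and 7.3.2.4 capture diversions during follow-up, so a repeat or revision could be counted. Little or no risk is as far as the text goes.

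**All-participant incidence is legitimate.** The primary objective concerns everyone chronically treated, and previously diverted people belong to that group. This stands: the crude figure can be reported. It is a different quantity from the incidence among those who can still have a first diversion, and the protocol does not separate the two.

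**Inconsistent classification.** A reader might infer that a diversion between first dose and enrolment would be an event for one participant and history for another. Table 1 does list both prior and concomitant surgery at baseline without saying what prior refers to. But section 7.3.1.1 starts the clock at odevixibat start, and both dates are collected, so the definition classifies such a diversion as on treatment. An explicit rule is useful; an actual contradiction is not shown.

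**Conclusion.** The concern holds for the diversion endpoints. As written, participants diverted before odevixibat enter as diversion-free and lower the crude diversion incidence by a factor of about (1 − f). On assumed values of f = 5–20% and a 10% incidence, the reported figure is 9.5% to 8.0%. This rests on their having no countable diversion; if repeats count, the factor is closer to 1.

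A reader might conclude that all the primary endpoints are biased in favour of odevixibat. The documents do not support this. Transplant-free and overall survival are not affected by this mechanism. For the composites that add death or transplant, the dilution is smaller, and its direction depends on the relative prognosis of the previously diverted, which is not given. The study has no comparator and no formal testing (section 7.9), and the shift is well inside the sampling error at 30 to 45 participants. The reason to correct it is that the endpoint's meaning is unclear and the correction is cheap.

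**What to change.** In sections 7.7.1 and 7.7.2.1, state that:

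- the diversion component of the incidence endpoint and diversion-free survival are analysed in participants with no biliary diversion before the first odevixibat dose, which is the time origin in section 7.3.1.1;
- previously diverted participants are tabulated separately, including any repeat or revision surgery, and stay in transplant-free and overall survival;
- a diversion between first dose and enrolment is classified for everyone by comparing the surgery date with the first-dose date.

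The cut-off should not be the consent date while the clock starts at first dose. A diversion after first dose and before consent is an on-treatment event under section 7.3.1.1, and dropping it would itself lower the incidence.

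The cost is a few sentences and a slightly smaller denominator for the diversion summaries. The dates needed are already collected, and no new assessment is required.
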